2 STUDY OBJECTIVES AND ENDPOINTS

2.1 Primary Objective

 To evaluate the safety of single and multiple ascending doses of orally administered AT-007 in healthy adult subjects and adult subjects with CG or GALK-deficient Galactosemia

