7.5 Analysis Populations

Two analysis populations will be defined:

• Screened Population (SP): The screened population will consist of all subjects who are screened independent if they were eligible or not.

- Randomized Population: The randomized population will consist of all subjects who are randomized to any cohort.
- Safety Population: The safety population will consist of all subjects who are randomized and receive at least 1 dose of study drug. All analyses will be performed according to treatment received. This population will be used for all analyses of safety data and biomarker data.
- Pharmacokinetic Population: The PK population will consist of all subjects who receive at least 1 dose of AT-007 and have sufficient concentration-time data to estimate at least one of the planned PK parameters, as determined by the study Pharmacokineticist. This population will be used for all analyses of PK.

For Parts D and E, the safety and PK population may be defined separately for the SAD and MAD periods.

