7.12 Analysis of Safety Data

7 12 1 General

The evaluation of safety will be based on the occurrence of treatment-emergent adverse events (TEAEs); discontinuations from study drug and/or the study because of AEs; clinical laboratory test results, physical examination findings, vital sign evaluations, and 12-lead ECGs results. All safety endpoints will be summarized descriptively. No statistical inference will be applied to the safety endpoints. Descriptive statistics will be calculated for quantitative safety data and frequency counts will be compiled for classification of qualitative safety data.

Safety measures including the baseline data will be summarized descriptively within each part (Parts A, B, C, D, E and D Extension) of the study by each cohort (dose level of AT-007 and placebo), pooled AT-007 group, and pooled placebo group.

For analyses of change from baseline, baseline will generally be defined as the predose assessment on Day 1 or Day -1, as scheduled. If this value is unavailable, the last nonmissing value prior to dosing will be used. Otherwise, missing observations will be treated as missing at random, and no data imputation will be performed. All data from the eCRFs, as well as any derived variables, will be presented in data listings.

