7.12.2 Adverse Events

All AEs will be coded to system organ class (SOC) and preferred term (PT) using MedDRA, Version 22.0 or later, and presented by subject data listings.

A treatment-emergent AE (TEAE) is defined as an AE that is not present prior to cohort with investigational product, but appeared following cohort or was present at cohort initiation but worsened during cohort. An AE that was present at cohort initiation but resolved and then

reappeared while the subject was on cohort is a TEAE (regardless of the intensity of the AE when the cohort was initiated). Programmatically, an AE will be classified as a TEAE if the start date and time occurs on or after the start date and time of first investigational product dosing.

The TEAE will be assigned to treatment based on the start date/time of occurrence.

The overall incidence of TEAEs (number and percentage of subjects) as well as the number of events will be summarized by cohort, severity grade, SAEs, causally related TEAE and SAEs, TEAEs leading to study or treatment discontinuation, life-threatening SAEs, and SAEs resulting in death.

The TEAEs will be summarized and tabulated at both the subject (number [%] of subjects) and event (number of events) level:

- By cohort, SOC, and PT
- By cohort, SOC, PT, and maximum reported severity
- By cohort, SOC, PT, and closest relationship to study drug

For the incidence at the subject level by SOC and PT, if a subject experiences more than 1 event within the same SOC and PT, only 1 occurrence will be included in the incidence.

For the incidence at the subject level by SOC, PT, and severity, if a subject experiences more than 1 event within the same SOC and PT, only the highest severity grade will be included in the incidence.

For the incidence at the subject level by SOC, PT and relationship to study drug; if a subject experiences more than 1 event within the same SOC and PT, only the most closely related occurrence will be included in the incidence.

Any SAEs, AEs with outcome of deaths, or AEs resulting in discontinuation of study or cohort will be presented.

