| Figure 14.2.7.1.1e | Plot of Mean (+/-SD) Plasma Galactitol Concentrations over Time – |
|--------------------|---|
| | Part E (PK Population) Plot of Mean (+/-SD) Plasma Galactose Concentrations over Time – |
| Figure 14.2.7.1.2e | Part E (PK Population) Plot of Mean (+/-SD) Whole blood Gal-1P Concentrations over Time |
| Figure 14.2.7.1.3e | - Part E (PK Population) |
| Table 14.2.7.2d | Summary of Plasma Galactitol Results by Subgroup (Gender) – Part D (Safety Population) |
| Table 14.2.7.2e | Summary of Plasma Galactitol Results by Subgroup (Gender) – Part E (Safety Population) |
| Table 14.2.7.3d | Summary of Plasma Galactitol Results by Subgroup (Age) – Part D (Safety Population) |
| Table 14.2.7.3e | Summary of Plasma Galactitol Results by Subgroup (Age) – Part E (Safety Population) |
| Table 14.2.7.4d | Summary of Plasma Galactitol Results by Subgroup (BMI) – Part D (Safety Population) |
| Table 14.2.7.4e | Summary of Plasma Galactitol Results by Subgroup (BMI) – Part E (Safety Population) |
| Table 14.2.7.5d | Summary of Plasma Galactitol Results by Subgroup (Enzyme Activity) – Part D (Safety Population) |
| Table 14.2.7.5e | Summary of Plasma Galactitol Results by Subgroup (Enzyme Activity) – Part E (Safety Population) |
| Figure 14.2.7.2d | Forest plot of Plasma Galactitol Results by Subgroup at Day 32– Part D (Safety Population) Forest plot of Plasma Galactitol Results by Subgroup at Day 32 – |
| Figure 14.2.7.2e | Part E (Safety Population) |
| Table 14.2.7.6d | Summary of Change in Allele due to Gene mutation – Part D (Safety Population) |
| Table 14.2.7.6e | Summary of Change in Allele due to Gene mutation – Part E (Safety Population) |
| Section 14.3 | Safety Data Summaries |
| Section 14.3.1 | Displays of Adverse Events |
| Table 14.3.1.1a | Overall Summary of Treatment-Emergent Adverse Events – Part A (Safety Population) |
| Table 14.3.1.1b | Overall Summary of Treatment-Emergent Adverse Events – Part B and Part C (Safety Population) |
| Table 14.3.1.1c | Overall Summary of Treatment-Emergent Adverse Events – Part B and Part C cohorts combined (Safety Population) |

| Table 14.3.1.1d | Overall Summary of Treatment-Emergent Adverse Events – Part D (Safety Population) Part D |
|----------------------------------|--|
| Table 14.3.1.1de | Overall Summary of Treatment-Emergent Adverse Events – Part D Extension (Safety Population) Part D Extension |

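### In Parts D and E the planned TEAE tables merge the single-dose and 27-dose periods, so neither a single-dose nor a multiple-dose TEAE incidence can be read from them

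*SAP*

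**What the plan says.** SAP 2.1 gives the primary objective as "To evaluate the safety of single and multiple ascending doses of orally administered AT-007", in healthy subjects and in both patient groups. Adverse events come first among the primary endpoints in SAP 2.4.

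Under SAP 3.1.4.4 and 3.1.4.5, a Part D or E subject takes a single dose on Day 1 and has a washout until the Day 6 predose point. Subjects who tolerated that dose, and for whom the Sponsor agrees, then take the same study drug daily from Day 6 through Day 32.

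The TEAE rules do not follow that structure:

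- SAP 7.12.1 summarises safety within each part "of the study by each cohort (dose level of AT-007 and placebo), pooled AT-007 group, and pooled placebo group".
- SAP 7.12.2 states: "The TEAEs will be summarized and tabulated at both the subject (number [%] of subjects) and event (number of events) level". It sets the basic tabulation as "By cohort, SOC, and PT". Two further tables add maximum severity and closest relationship. A subject counts once per SOC and PT, at the highest severity or closest relationship.
- The TEAE clock is single: "Programmatically, an AE will be classified as a TEAE if the start date and time occurs on or after the start date and time of" the first investigational product dose.
- Attribution is by treatment: "The TEAE will be assigned to treatment based on the start date/time of occurrence".
- SAP 8 lists one set of TEAE tables for Part D and one for Part E. The first is titled "Overall Summary of Treatment-Emergent Adverse Events – Part D (Safety Population) Part D".

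The only provision for a split is in SAP 7.5: "For Parts D and E, the safety and PK population may be defined separately for the SAD and MAD periods". Protocol 9.2.2 has the same optional wording.

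**The concern.** One dose and 27 consecutive doses are different regimens, and a decision on tolerability lies between them. The primary objective names both, so a reader would expect an AE summary of each in patients. As written, the plan gives one percentage per cohort covering the Day 1 dose, the washout, multiple dosing and follow-up.

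The same SAP does split secondary outputs. Dose proportionality in Parts D and E has separate single-dose and multiple-dose tables (14.2.6d1/d2 and e1/e2), and so do the individual PK-parameter listings (for example 16.2.6.1d1/d2). The primary endpoint gets less resolution than a secondary one.

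At stake is whether the report's AE tables answer the primary objective for patients as prespecified, or whether someone must rebuild the answer from listings after the data are known.

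**Working it through.** **Inputs**

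- Part D: 3 cohorts of 6, each with 4 active and 2 placebo (SAP Table 3-5).
- Multiple dosing: Day 6 through Day 32 (SAP 3.1.4.4).
- EOS visit: Day 60 (Protocol Appendices D and E).
- Safety population: randomized, with at least one dose (SAP 7.5).
- Number who never start multiple dosing: not given. Assumed to be 0, 1 or 2 of the 4 active subjects in a cohort.

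**The plan's own figures**

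- Part D size: 3 × 6 = 18, as stated (12 active, 6 placebo).
- Multiple doses: 32 − 6 + 1 = 27, as stated.

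**What the merged window contains**

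- Single-dose window: Days 1 to 5 = 5 days and 1 of 28 doses.
- From Day 6 to Day 60: 60 − 6 + 1 = 55 days and 27 of 28 doses.
- Single-dose share of the window: 5/60 = 8.3%.

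The merged figure mostly reflects multiple dosing, so the single-dose result is the harder one to see.

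**Does any rule separate the periods?**

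- Assigning a TEAE to treatment by onset does not, because both periods use the same study drug.
- The TEAE definition does not, because it has one start point.
- The option in SAP 7.5 could, but no AE output is tied to it.

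**What is lost when everyone advances**

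Let s and m be the numbers of subjects with a TEAE in the single-dose and multiple-dose periods, and o the number with a TEAE in both. The merged count is s + m − o. With n = 4, s = 2 and m = 2, o can be 0, 1 or 2:

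- o = 2 gives 2/4 = 50%
- o = 1 gives 3/4 = 75%
- o = 0 gives 4/4 = 100%

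The same pair of period results gives three different merged figures, and a merged figure cannot be taken apart again. The once-per-subject rule adds to this. A mild event after the single dose and a moderate recurrence on Day 20 become one moderate entry at subject level.

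**Denominator, if someone does not advance**

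One affected multiple-dose subject is 1/n on the merged denominator and 1/(n − k) among those who took a multiple dose, where k is the assumed number who never started:

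| Active subjects | k | Merged | Multiple-dose only |
|---|---|---|---|
| 4 (one cohort) | 0 | 25.0% | 25.0% |
| 4 | 1 | 25.0% | 33.3% |
| 4 | 2 | 25.0% | 50.0% |
| 12 (Part D pooled) | 0 | 8.3% | 8.3% |
| 12 | 1 | 8.3% | 9.1% |
| 12 | 2 | 8.3% | 10.0% |

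With k = 0 the two denominators are identical.

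**The case against.** The case against has real force.

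**The information is not lost to the study.** AE start date and time are collected (SAP 3.2.1). All AEs and dosing records are listed by subject. With 4 active subjects per cohort, events on Days 1 to 5 can be told from later ones by eye. Laboratory, vital-sign and ECG summaries are by time point (SAP 7.12.3 to 7.12.5), so those parts of the primary endpoint are not merged. A reader might infer that safety of single and multiple dosing cannot be assessed in patients at all. The documents do not support that: the gap is confined to the TEAE summary tables.

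**No multiple-dose TEAE rate is planned.** A reader might infer that multiple-dose rates use the wrong denominator. They do not, because the SAP plans incidence among everyone dosed, and the safety population is right for that quantity. The shift in the table above arises only if the merged figure is read as a multiple-dose rate and someone did not advance.

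**Single-dose intolerance is not hidden.** AEs leading to discontinuation are summarised and listed (Tables 14.3.2.3d and e), and disposition gives reasons for stopping.

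**Table titles prove little.** The Part D PK-parameter summary also has a single title (Table 14.2.2d), yet SAP 7.10 reports those parameters by day. This is fair, but for TEAEs the text itself names no period or day, so here the text and titles agree.

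**The SAP already permits a split.** It does, and every AE table runs on the safety population, so the option would carry through if used. But leaving it optional leaves the choice open until the data are seen.

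Safety is descriptive, and escalation rests on the SRC's review rather than on these tables. No alpha, power or sample-size figure is affected.

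**Conclusion.** The point holds as a reporting gap in eight tables. As planned, the Part D and E TEAE tables give one mixed incidence per arm, although the primary objective names two dosing regimens. Neither regimen's incidence can be read from those tables; both can be rebuilt from the listings.

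The loss exists even if every subject advances: with 2 of 4 affected in each period, the merged figure ranges from 50% to 100%. The denominator effect is conditional. It is zero with no non-advancers, and moves one event in four from 25% to 33% or 50% if one or two active subjects in a cohort do not start multiple dosing. That range is an assumption, because the documents do not say whether anyone failed to advance.

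The change should be made because it is nearly free and lets the prespecified tables answer the primary objective. It does not call the study's safety conclusions into question.

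**What to change.** In SAP 7.5, change *may* to *will* for the safety population in Parts D and E. In SAP 7.12.2 and Tables 14.3.1.1 to 14.3.1.4, d and e, add SAD and MAD columns beside the overall column, assigning TEAEs by start date and time.

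- **SAD:** onset from the Day 1 dose to before the first multiple dose. For subjects who never start multiple dosing, use the same Day 6 cut-off, so that the window does not lengthen for those who tolerated the drug poorly. Their later events stay in the overall column, flagged. Denominator: all subjects dosed on Day 1.
- **MAD:** onset from the first multiple dose to EOS. Denominator: subjects with at least one multiple dose.
- **Events spanning both periods:** identify in the listing any event that starts in SAD and continues into MAD. Do not build a column on worsening, because SAP 3.2.1 lists start, stop and severity but no date of worsening.
- **Footnote:** the SAD window of about 5 days is shorter than Part A follow-up, which runs to a visit 28 days after the dose, so the two incidences are not directly comparable.

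The cost is SAP wording and a few extra columns in eight tables. No new data are needed.

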7.12.3 Clinical Laboratory Assessments

Observed and change from baseline of continuous clinical laboratory values (serum chemistry, hematology, coagulation, and urinalysis) for each parameter will be summarized by Part and cohort at each scheduled nominal time point. The number and percentage of subjects with shift changes from baseline based on the laboratory normal ranges will be tabulated. Laboratory data will be listed by subject at each time point. Clinical laboratory values that are out of normal ranges will be presented in a separate listing. Urinalysis laboratory tests will be presented in data listings only.

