The SRC will make recommendations to the Sponsor regarding dose escalation or de-escalation for each cohort based on the results from the previous cohort as described in [Section 3.4](#). The Sponsor will act upon this recommendation and inform the Investigator(s) and the IRB(s)/IEC(s).

The SRC will pay particular attention to DLTs defined as any AT-007-related AE or clinically relevant finding on laboratory tests, ECGs, vital signs, or physical examinations that, in the opinion of the Investigator and/or the SRC, precludes administering the dose to any subject and/or continuing to administer daily doses to the subject who experienced the event. Specific individual subject-level dose stopping criteria for hepatic and renal toxicity are described in [Appendix G](#) and [Appendix H](#). For DLTs, as well as fatal serious adverse events (SAEs) and life-threatening SAEs, breaking the blind will be considered and initiated (as needed) per SRC discussion and agreement.

Dose-escalation will be stopped and de-escalation initiated if:

- ≥ 2 subjects on AT-007 (B and C cohorts of the same dose level considered together) experience a DLT at any time through 24 hours after the last dose of study treatment
- Any subject on AT-007 has a fatal SAE or life-threatening SAE requiring urgent intervention at any time through 24 hours of the last dose of study treatment

The maximum tolerated dose (MTD) will be the dose level below the dose level at which one or more of the events listed above occurs.

Dose escalation within each part of the study will continue until the MTD is identified per the rules described earlier in this section or the SRC and/or Sponsor decide to stop dose escalation. Dose de-escalation, if initiated within any part of the study, will continue until the MTD is identified or the SRC and/or Sponsor decide to stop.

If the events outlined in the above MTD definition do not occur at any dose level in a study part, then the MTD will be the highest dose level in that study part.

If the events outlined in the above MTD definition occur at any given dose level, the Sponsor may decide to investigate a dose higher than the previously well-tolerated dose but lower than the dose at which one of the events outlined in the above MTD definition occurred.

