4.2.2. Exclusion Criteria

1. History or presence of clinically significant hematopoietic, hepatic, endocrine, metabolic (other than CG), pulmonary, neurological (other than CG-related), psychiatric, immunological, dermatological, or gastrointestinal diseases; conditions capable of altering the absorption, metabolism, or elimination of drugs; or conditions that constitute a risk factor when taking the study drug and/or impact the conduct or results of the study.
2. Evidence of diagnosis of clinical variant Galactosemia.
3. Complications of CG resulting in disability that, in the opinion of the Investigator, may prevent the subject from completing all study requirements (e.g., severe neurological deficits, severe cognitive impairment, or severe language difficulty).
4. Impaired renal function or eGFR < 90 mL/min/1.73 m², or urine protein-to-creatinine ratio (UPCR) ≥ 200 mg/g, or urine albumin-to- creatinine ratio (UACR) (≥ 30 mg/g. Note: eGFR and UPCR/UACR are an estimation of renal function, and the ultimate decision of whether a patient has normal renal function (and can be included in the study) is at the discretion of the Investigator, assuming there are no safety concerns. Also, because eGFR, UPCR and UACR can vary day to day based on outside factors, patients can be re-screened for eGFR, UPCR and UACR multiple times to understand the renal function of the patient.
5. History or presence of significant cardiovascular disorders including myocardial infarction, stroke, uncontrolled hypertension (sitting blood pressure ≥140/90 mmHg), left ventricular (LV) hypertrophy, atrial fibrillation, or valvular heart disease.
6. Abnormal findings on the screening 12-lead ECG, such as ST/T wave changes of ischemia, pathological Q wave changes, or any rhythm other than normal sinus rhythm.
7. Evidence of significant active hematological disease and/or cumulative blood donation of 1 unit (500 mL) or more including blood drawn during clinical studies in the last 3 months.
8. Unwilling to comply with a galactose-restricted diet.
9. Positive urine screen for drugs of abuse (amphetamines, barbiturates, benzodiazepines, cocaine, cannabinoids, opiates) unless clinically indicated.

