- Discharge subject from the CRU and remind the subject/caregiver to fast overnight for at least 10 hours and return to the CRU (before either taking study drug or breaking the fast) on the morning of Day 30

6.8.3. Day 30, and Day 60

These visits may be done as either home health visits or as in-clinic visits. The visits should start in the morning. Procedures for these 2 visits are the same.

The following procedures will be done before study drug administration:

- Collect and record unused study drug and review study drug diary card
- Perform physical examination including weight
- Measure predose vital signs
- Conduct predose 12-lead ECG
- Collect predose blood sample for PK
 - This should be done 24 hours (± 15 minutes) after the dose administered on the previous day (Day 29 and Day 59, respectively).
- Collect predose blood sample for analysis of biomarkers of galactose metabolism including galactose, galactitol, and galactose-1-p

- This should be done 24 hours (± 15 minutes) after the dose administered on the previous day (Day 29 and Day 59, respectively).
- For female subjects of childbearing potential only, urine pregnancy test (pregnancy test must be negative for the subject to receive study drug)

Then, study drug (AT-007 or placebo) will be administered to the subject, and the following procedures will be done after the dose:

- Collect fasting blood sample(s) for clinical laboratory testing (hematology, coagulation and biochemistry)
- Collect fasting urine sample for urinalysis, UACR and UPCR
- Conduct postdose 12-lead ECG
- Measure postdose vital signs
- Collect postdose blood samples for PK
- Collect postdose blood samples for analysis of biomarkers of galactose metabolism including galactose, galactitol, and galactose-1-p
- Schedule the next visit
- Dispense study drug for the time between this visit and the next visit
- Remind the subject/caregiver that study drug should be taken QD under fasting conditions at approximately the same time of day as on Day 1 and to record the date/time of each dose on the study drug diary card ([Section 5.3](#))
- Remind the subject/caregiver to fast overnight for at least 10 hours and return to the CRU (before either taking study drug or breaking the fast) on the morning of the next visit

Adverse event and concomitant medication data will be collected both before and after dose administration.

6.8.4. Day 90 (Check-in for Second In-clinic Period and Last Study Drug Dosing Day)

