7.1.2. Clinical Laboratory Tests

Blood and urine samples for routine clinical laboratory tests will be collected at the visits as indicated in the Schedules of Assessments for Parts A, B, C, D, E, and D Extension ([Appendix A](#), [Appendix B](#), [Appendix C](#), [Appendix D](#), [Appendix E](#), and [Appendix F](#), respectively).

A Clinical Laboratory Improvement Amendments (CLIA) certified laboratory will perform the following clinical laboratory tests:

- Hematology: hemoglobin, hematocrit, total and differential leukocyte count, RBC, and platelet count
- Serum Chemistry: albumin, blood urea nitrogen (BUN), creatinine, total bilirubin, alkaline phosphatase (ALP), aspartate transaminase (AST), alanine transaminase (ALT), sodium (Na⁺), potassium (K⁺), chloride (Cl⁻), lactate dehydrogenase (LDH), calcium (Ca), uric acid, glucose, direct bilirubin (DB), and gamma-glutamyl transferase (GGT)
- Coagulation: prothrombin time (PT) and international normalized ratio (INR)
- Serology: blood tests for hepatitis B surface antigen, hepatitis C antibody, and HIV
- Urinalysis by an automated or manual urine “dipstick” method: pH, specific gravity, protein, glucose, ketones, bilirubin, blood, nitrite, leukocyte esterase, and urobilinogen. If protein, occult blood, nitrite, or leukocyte esterase values are out of range, a microscopic examination will be performed.
- Urine Drug Screen: drugs of abuse (amphetamines, benzodiazepines, barbiturates, cannabinoids, cocaine, opiates)
- Urinary markers of renal function: UACR and UPCR
- Urine cotinine screen (subjects in Parts A, B, and C only)

- Pregnancy test (all female subjects of childbearing potential)
- FSH (for female subjects claiming postmenopausal status)

For Parts D, E, and D Extension only, the following tests will be done in addition to the ones listed above:

- GALT (Part D and Part D Extension but only done once for subjects participating in both Parts) or GALK (Part E) activity in red blood cells
- GALT (Part D and Part D Extension but only done once for subjects participating in both Parts) or GALK (Part E) gene analysis
- Aldose Reductase activity (only done once for subjects participating in both Parts D and D Extension)

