- j: Samples for clinical safety laboratory tests (hematology, chemistry, coagulation, urinalysis, UACR and UPCR) will be collected under fasting conditions. At the Screening visit only (i.e., only applicable to subjects for whom this visit is required and does not need to be repeated at screening if already done at prescreening), HIV and hepatitis B & C testing will also be done. Hematology, chemistry, and coagulation at the Screening visit (i.e., only applicable to subjects for whom this visit is required) does not need to be repeated if already done at prescreening and prescreening was within 60 days before the first dose of Part D Extension study drug. Clinical safety laboratory tests (hematology, chemistry, coagulation, urinalysis, UACR and UPCR) do not need to be repeated at Day -1 if already done at prescreening or screening and the prescreening/screening visit was done within 60 days before the first dose of Part D Extension study drug.
- k: Serum pregnancy tests will be done at Screening (if applicable), Day -1 (also urine test if serum test cannot be processed immediately), and EOE visits; urine pregnancy tests will be done at all other time points. From Days 1 through 90, pregnancy tests must be done (and the result negative) on dosing days before study drug is administered. A pregnancy test must be performed on Day -1 even if already performed earlier during the screening period.
- m: On Days 1, 2, and 90, study drug will be administered at the clinic. On Days 30 and 60, study drug will be administered during the visit (home health or in-clinic). All other doses of study drug will be taken at home QD with water in the morning (preferably after an overnight fast of ≥ 10 hours with the fast broken ≥ 2 hours after the dose). Study drug administration should be at approximately the same time of day (preferably 8 am) throughout the extension. Drug accountability (including dispensing and/or collecting) will be assessed at all visits during the 90 days of dosing.
- n: On Day 1, a predose (within 60 minutes before the dose) blood sample for PK will be collected. On Days 30, 60, and 90, blood samples for PK will be collected predose (24 hours [± 15 minutes] after the dose taken the day before and within 60 minutes before the dose administered on that day) and at 2, 4, 8, and 12 hours (± 5 minutes for all time points) after the dose. An additional sample will be taken on Day 91 at 24 hour after the Day 90 dose.

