APPENDIX H. GUIDANCE IN CASE OF WORSENING RENAL FUNCTION

Renal function must be closely monitored during the study, particularly during administration of potentially nephrotoxic drugs, such as acetaminophen, non-steroidal anti-inflammatory drugs (NSAIDs), fluoxetine, antihistamines, antimicrobials, benzodiazepines, proton pump inhibitors, phenytoin, trimethoprim, fenofibrate, cimetidine, cephalosporins, probenecid, aminoglycoside, amphotericin, ketoconazole, and clofibrate

Urine protein-to-creatinine ratio (UPCR), urine albumin-to- creatinine ratio (UACR) and eGFR will be assessed at each visit. In case of increased UPCR (≥ 200 mg/g), increased UACR (≥ 30 mg/g), eGFR < 30 mL/min/1.73 m², or decreased eGFR $> 30\%$ compared to baseline, a retest must be performed within 24 hours and if the abnormal laboratory result is confirmed, the following actions will be taken:

- The event must be reported to the Sponsor within 24 hours
- Concomitant medications will be reviewed and any potentially nephrotoxic drug must be discontinued
- Recent medical history will be investigated specifically for significant increase or decrease of blood pressure, plasma volume depletion, flu-like symptoms, urinary tract infection, and abdominal pain suggestive of obstructive uropathy.
- If there is no suspected concomitant medication , or if no improvement of renal function is observed after 72 hours of discontinuation of the potentially nephrotoxic drug, and if there is nothing in recent medical history that is likely to cause the abnormal renal function, the study drug will be temporarily discontinued.
- The following urinary markers of kidney injury must be measured: Clusterin (CLU), Cystatin-C (CysC), Kidney Injury Molecule-1 (KIM-1), N-acetyl-beta-D-glucosaminidase (NAG), Neutrophil gelatinase-associated lipocalin (NGAL), and Osteopontin (OPN)
- A renal ultrasound will be performed.
- A nephrologist will be consulted
- Renal function (eGFR, UPCR and UACR) will continue to be monitored every 48 hours until stabilization, then every 2 weeks until normalization.
- At this time, the Investigator in consultation with the nephrologist will decide if the study drug may resume

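### The SAP derives no eGFR and counts subjects by laboratory change only as normal-range shifts, so a modest crossing of the protocol's 30% eGFR threshold can tabulate as normal to normal

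*SAP*

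**What the plan says.** Protocol Appendix H states that urine protein and albumin ratios are followed throughout: "creatinine ratio (UACR) and eGFR will be assessed at each visit". One of its triggers reads "or decreased eGFR $> 30\%$ compared to baseline, a retest must be performed within 24 hours". The others are UPCR of at least 200 mg/g, UACR of at least 30 mg/g, and eGFR below 30. If the retest confirms the result, the sponsor is told within 24 hours, nephrotoxic co-medication is stopped and a work-up follows. Study drug is interrupted temporarily if no other explanation is found. Protocol 3.5 refers to this appendix and Appendix G: "Specific individual subject-level dose stopping criteria for hepatic and renal toxicity are described in". Protocol 4.2.2 excludes "Impaired renal function or eGFR < 90 mL/min/1.73", subject to investigator discretion.

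Protocol 7.1.2 adds "Urinary markers of renal function: UACR and UPCR" to the laboratory list. In the Part D Extension, Days 30, 60 and 90 include "Collect fasting urine sample for urinalysis, UACR and UPCR" as well as chemistry.

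SAP 7.12.3 plans four things:
- summaries of continuous values and change, by Part and cohort;
- the shift count: "The number and percentage of subjects with shift changes from baseline based on the laboratory normal ranges will be tabulated";
- full listings by subject;
- a separate listing of out-of-range values.

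SAP 7.1 leaves unscheduled and repeat values out of safety summaries but keeps them in listings. eGFR, UACR and UPCR appear nowhere in the SAP's laboratory list (3.2.2), methods or table shells. SAP section 1 ties the plan to protocol V6.0.

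**The concern.** Laboratory safety is part of the primary endpoint, and the protocol names a specific renal change on which it acts. The entry floor of 90 mL/min/1.73 m² favours subjects with low or mid-normal creatinine. In them creatinine can rise enough to cut eGFR by more than 30% and still lie below the laboratory's upper limit. The shift table then reads normal to normal, and the value does not reach the out-of-range listing.

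What would be missing is a reported count, AT-007 against placebo, of subjects who crossed the protocol's own threshold. A report showing no creatinine shifts could be read as showing no crossings, which does not follow. This matters most in the Part D Extension. It has 90 days of dosing, 3:1 randomization against placebo, repeated renal measurements, and its own output set and CSR addendum (SAP 4 and 7.1).

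**Working it through.** **Inputs from the documents.** The trigger is eGFR below 0.70 × baseline (Appendix H) and the entry floor is eGFR 90 (Protocol 4.2.2). The shift rule uses the laboratory normal range (SAP 7.12.3). The plan gives no figure to reproduce.

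**Assumptions.** The documents give no eGFR equation (MDRD appears only in the protocol's abbreviation list) and no creatinine limits. I use MDRD, CKD-EPI 2009 and CKD-EPI 2021 at age 25. The assumed upper limits are 1.0–1.1 mg/dL for women and 1.2–1.3 for men.

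**Step 1: creatinine rise that gives a 30% fall.** Under MDRD eGFR varies as creatinine to the power −1.154, so the ratio is 0.70^(−1/1.154) = 1.362. Above their knot the CKD-EPI equations give 1.343 and 1.346; below it a larger rise is needed. A woman at 0.7 reaches 0.94–0.95 and a man at 0.8 reaches 1.09–1.18. Both stay in range. Their baseline eGFRs are 102–123 and 118–126, so both meet the entry floor.

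**Step 2: size of the gap.** The eGFR fall at which creatinine just reaches the upper limit is, under MDRD, 1 − (baseline/limit)^1.154. For a woman at 0.7 with limit 1.0 this is 1 − 0.7^1.154 = 33.7%. For a man at 0.8 with limit 1.2 it is 1 − (0.8/1.2)^1.154 = 37.4%. Falls between 30% and the tabulated value are not counted; a value below 30% means no gap.

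| Baseline creatinine (mg/dL) | Limit | MDRD | CKD-EPI 2009 | CKD-EPI 2021 |
|---|---|---|---|---|
| Woman 0.6 | 1.0 | 44.5% | 38.2% | 37.2% |
| Woman 0.6 | 1.1 | 50.3% | 45.0% | 44.0% |
| Woman 0.7 | 1.0 | 33.7% | 35.0% | 34.8% |
| Woman 0.7 | 1.1 | 40.6% | 42.1% | 41.9% |
| Woman 0.8 | 1.0 | 22.7% | 23.6% | 23.5% |
| Woman 0.8 | 1.1 | 30.8%* | 32.0% | 31.8% |
| Man 0.7 | 1.2 | 46.3% | 36.3% | 34.4% |
| Man 0.7 | 1.3 | 51.1% | 42.2% | 40.4% |
| Man 0.8 | 1.2 | 37.4% | 32.7% | 31.7% |
| Man 0.8 | 1.3 | 42.9% | 38.9% | 37.9% |
| Man 0.9 | 1.2 | 28.3% | 29.4% | 29.2% |
| Man 0.9 | 1.3 | 34.6% | 35.9% | 35.7% |
| Man 1.0 | 1.2 | 19.0% | 19.8% | 19.7% |
| Man 1.0 | 1.3 | 26.1% | 27.2% | 27.0% |

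*MDRD baseline eGFR is 87 here, below the entry floor.

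Sensitivity: if eGFR is simply proportional to 1/creatinine, a woman at 0.7 with limit 1.0 gives 1 − 0.7/1.0 = 30.0%, so no gap. A man at 0.8 with limit 1.2 gives 33.3%.

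**Step 3: the other eGFR trigger.** An eGFR of 30 needs creatinine of about 1.7–2.4 (women) or 2.2–3.0 (men) over ages 18 to 65. That is out of range under every assumed limit, so this trigger is caught.

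**Step 4: can the change summary stand in?** No. A maximum creatinine change of +0.30 mg/dL is a 34–35% fall for a woman at 0.7 but only 26–27% for a man at 1.0.

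**Step 5: would a shift table on eGFR be enough?** Not reliably. 0.70 × 100 = 70 and 0.70 × 120 = 84, both still normal if the laboratory's range starts at 60.

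**The case against.** The strongest reply is that this is version lag. The SAP follows V6.0, while the supplied protocol is evidently later: up to 28 Extension subjects (Protocol 3.3.6) against 16 (SAP 3.1.4.6), and 60-day against 40-day Extension screening. V6.0 is not available, so nothing shows that the 30% trigger existed when SAP 7.12.3 was written. That stands. One cannot infer that the SAP contradicted its own protocol, only that it has not been realigned.

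Second, Appendix H is guidance for managing subjects, and Protocol 9.2.7 promises only descriptive safety summaries. No section promises a count of crossings. That is true. But Protocol 9.2.7 leaves the detail to the SAP, and the shift table as written can show no renal change after a crossing.

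Third, much is recorded elsewhere. All values are listed and creatinine change is summarized. A crossing may also be reported as an adverse event (Protocol 8.1.1), with drug interruption recorded (SAP 3.2.1). If laboratories transfer eGFR as a parameter, SAP 7.12.3 would summarize its change. So a reader should not infer that the data are lost. None of these routes applies the threshold, however, and Appendix H requires a sponsor report, not an adverse event entry.

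Fourth, the exclusion of repeat values in SAP 7.1 has limited effect. It mainly removes the confirming retest; a trigger value from a scheduled visit stays in the summaries.

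Finally, the term in Protocol 3.5 invites the reading that every crossing stops dosing. Appendix H makes interruption temporary and conditional on finding no other cause.

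**Conclusion.** The point holds in a limited form and is worth considering at low priority. No planned output applies the 30% eGFR threshold or summarizes the collected UACR and UPCR. Under the assumed equations and limits, the uncounted range runs from 30% to about 32–43% for a woman at 0.7 or a man at 0.8 mg/dL. It is wider at lower baselines, and narrow or nil for a woman at 0.8 and for men at 0.9 or above. Other equations or local limits would move these figures.

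A reader might infer that subjects are less well protected, or that serious renal decline would go unreported. The documents support neither. Appendix H operates at the site independently of the SAP, larger falls move creatinine out of range, and eGFR below 30 is always flagged under the assumed limits. What is affected is the reporting of a primary safety endpoint.

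**What to change.** Amend SAP 7.12.3, first for the Part D Extension output set:
- Name one eGFR equation and derive eGFR from collected creatinine, age and sex. Use the SAP 7.1 baseline, stating that in the Extension it may be a screening value up to 60 days old.
- By cohort, pooled AT-007 and pooled placebo, report the number (%) of subjects with any on-treatment eGFR more than 30% below baseline. Include unscheduled values as a stated exception to SAP 7.1, and show retest-confirmed crossings separately.
- Add counts of UPCR of at least 200 mg/g and UACR of at least 30 mg/g where collected: Extension Days 30, 60, 90 and EOE; Part A Day 3 and EOS (Appendix A, Protocol 6.9); EOS in the other Parts.
- List these subjects with the retest result and any drug interruption. Note that the central derivation may differ from the site values that triggered Appendix H, since local laboratories may be used (Protocol 10.5).

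The cost is a SAP amendment with a few extra tables and listings per Part, and no new samples or visits. The counts are too small for inference: 0 of 21 active subjects has a one-sided 95% upper limit of 1 − 0.05^(1/21) = 13%, and 0 of 7 on placebo 1 − 0.05^(1/7) = 35%. They should be descriptive only.
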